5.1.2. Blinded Sample Size Re-estimation

A bSSR procedure will be utilized to ensure that the trial has an appropriate sample size to achieve the pre-specified power. This procedure is blinded, in that it does not use information on treatment assignments. Only pooled data from a blinded snapshot will be used to estimate the variance of the primary endpoint. Based on the estimated variability, the final study size will be calculated. The allowable range of the final sample size is constrained in a pre-specified manner, subject to the planned and maximum sample size. The bSSR procedure described below was evaluated via simulation and is efficient in determining the appropriate sample size under a range of possible scenarios without inflating type 1 error. The methodology and implementation details are described below.

The bSSR procedure has four steps,

- 1) At a blinded snapshot, a Bayesian predictive model will use the available data to generate predictions (multiple imputations) of all future HbA_{1c} data yet to be observed in the trial using the available data at the snapshot (see Section 5.1.2.2).

- 2) These predicted datasets will each be analyzed using the primary analysis model. The residual errors from each model will be used to determine a predictive distribution of the total variability of change in HbA_{1c} from baseline to the end of the study.
- 3) The predictive distribution of the variability will be used to determine the recommended sample size.
- 4) The study team will consider the recommended sample size and decide on the final sample size.

For practical reasons, the final sample size is constrained by a pre-specified minimum, N_{\min} , and maximum, N_{\max} . Therefore if the estimated final sample size is greater than N_{\max} , 400 is recommended. If the estimated final sample size is less than N_{\min} , 258 is recommended. The resulting estimated sample size is a recommendation, is non-binding, but represents the model estimate of the appropriate sample size. The final decision on the sample size would be subject to constraints from the maximum and minimum sample sizes. Factors influencing the final sample size are described in Section 5.1.2.4.

5.1.2.1. Traditional Power Analysis versus Blinded SSR for a Non-Inferiority Trial

When powering a non-inferiority trial, assumptions need to be made to determine the sample size for a pre-specified type I (α) and type II (β) error level. The non-inferiority margin is denoted as δ , the assumed difference is μ , the fraction dropping out of the study is f , and the assumed standard deviation of the outcome variable is σ . Putting this together the total number of patients to enroll (to ensure that the completers have the pre-specified power) for the trial can be estimated by,

$$N = 4 * \frac{(Z_{1-\alpha} + Z_{1-\beta})^2}{(\mu - \delta)^2 / \sigma^2} \left(\frac{1}{1 - f} \right).$$

When there is considerable uncertainty in the value of σ , a conservative assumption may be made, such that it is assumed to be sufficiently large to cover the range of the literature. This leads to larger sample sizes than are needed to achieve the desired level of confidence in the objective of interest.

Blinded SSR will be used to determine the sample size necessary to achieve the desired power using data from a blinded snapshot. These data will be used to estimate σ , denoted $\hat{\sigma}$. The sample size is estimated, \hat{N} , using,

$$\hat{N} = 4 * \frac{(Z_{1-\alpha} + Z_{1-\beta})^2}{(\mu - \delta)^2 / \hat{\sigma}^2} \left(\frac{1}{1 - f} \right)$$

with $\alpha = 0.025$ (one-sided), $\beta = 0.05$, $\mu = 0$, $\delta = 0.4\%$, $f = 0.15$. Blinded SSR is most effective in the cases where the therapies are expected to have similar effects, $\mu \approx 0$. Since this assumption is valid in this study, i.e. both treatments are expected to have similar mean responses, the data could be pooled to estimate variability.

5.1.2.2. Timing and Data used for the Blinded SSR

When approximately 40% of the pre-specified minimum subjects have been enrolled in the study and finished 24-weeks of treatment, or about 6 months prior to the completion of enrollment, depending on which occur first by team assessment, a blinded snapshot of the study data will be used to estimate the necessary final sample size. The snapshot will contain a scrambled patient identifier that is unique to each patient (but different than their unique subject identifier used in the study), the HbA_{1c} values corresponding to each patient visit, the country of enrollment of the patient, and an indicator of whether the patient dropped out, completed, or is currently ongoing in the study, and other stratification factors. This information will be modeled to estimate the variability in HbA_{1c} at the final visit and therefore inform the decision on final sample size. The treatment assignment will not be provided in the data snapshot and will not be used to estimate variability.

5.1.2.3. Blinded SSR Methodology

At the time of the blinded SSR, all available HbA_{1c} data in the database will be used. The HbA_{1c} value for subject i , and time t_j is denoted as y_{ij} , the total duration of the study is d , the subject random effect is, s_i , and the residual error is, ϵ_{ij} . The model for HbA_{1c} a Bayesian Integrated Two-Component Prediction (ITP) (Fu, 2010) and is written as,

$$y_{ij} = (\theta + s_i + \epsilon_{ij}) \frac{(1 - e^{-kt_j})}{(1 - e^{-kd})}$$

with the between subject error,

$$s_i \sim N(0, \sigma_b^2),$$

and within subject error,

$$\epsilon_{ij} \sim N(0, \sigma_w^2).$$

This model is Bayesian and requires specification of prior distributions for each parameter. For each parameter, non-informative priors have been chosen,

$$k \sim \text{Uniform}(0.001, 10),$$

$$\theta \sim N(-1, 1000),$$

$$\sigma_b^2 \sim \text{IG}(0.01, 0.01),$$

and

$$\sigma_w^2 \sim \text{IG}(0.01, 0.01).$$

This Bayesian model will be fit using Markov Chain Monte Carlo (MCMC) with the OpenBUGS package in R. The MCMC algorithm will use one chain, with initial values for the parameters drawn from their corresponding prior distributions. An appropriate burn-in period will be used of at least 10,000 iterations to ensure that the MCMC chain has reached convergence. After the burn-in period, 10,000 MCMC samples will be obtained for all parameters in the model, as well as all missing y data. Therefore each MCMC sample contains a complete predicted dataset,

where all unobserved y data are imputed. These 10,000 predicted datasets will be used to estimate the variability in HbA_{1c}. To ensure independence of the MCMC samples, the chains will be thinned by at least 10 to ensure that the 10,000 selected samples are not highly correlated. Diagnostics will be assessed to ensure convergence of the chain.

For each of the 10,000 MCMC samples, the primary analysis described in Section **Error! Reference source not found.** (containing all terms other than treatment assignment), will be performed using the complete dataset corresponding to each imputation step. For each of these k analyses, $k=1$ to 10,000, the total variability will be estimated, as $\hat{\sigma}_{T,k}$ by evaluating the residual error of the model. For each value of $\hat{\sigma}_{T,k}$, the estimated sample size will be computed using the sample size formula introduced in the previous section for a non-inferiority trial,

$$\hat{N}_k = 4 * \frac{(Z_{1-\alpha} + Z_{1-\beta})^2}{(\mu - \delta)^2 / \hat{\sigma}_{T,k}^2} \left(\frac{1}{1-f} \right)$$

with $\alpha = 0.025$ (one-sided), $\beta = 0.05$, $\mu = 0$, $\delta = 0.4\%$, $f = 0.15$. The mean value of the 10,000 \hat{N}_k values, \bar{N} as well as the distribution of \hat{N}_k will be reported. The recommended sample size, \hat{N} , is then subject to constraints from the maximum and minimum sample sizes, using.

$$\hat{N} = \min(\max(\bar{N}, N_{\min}), N_{\max})$$

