5.1. Determination of Sample Size

5.1.1. Sample Size Section from the Protocol

Based on the primary objective, to show noninferiority of LY2963016 to Lantus® at the 0.40% noninferiority margin (NIM), 109 completers per arm (218 total) are needed at 24 weeks. This calculation assumes no treatment difference in HbA1c between LY2963016 and Lantus®, a common standard deviation (SD) of 1.05% for change from baseline in HbA1c, a two-sided significance level of 0.05, and over 80% power. Assuming a 15% dropout rate at 24 weeks, the required number of randomized patients is 129 per arm (258 total). This sample size is noted as the minimum sample size required in the study.

Blinded sample-size reestimation (bSSR) may be performed when approximately 40% of the subjects have been enrolled in the study and finished 24-weeks of treatment, or about 6 months prior to the completion of enrollment, depending on which occur first by team assessment. This reestimation will use a statistical model to estimate the variability in the change in HbA1c from baseline to 24 weeks using all available patient HbA1c values at the time of data cutoff. The estimate of variability will then be used to recalculate the sample size that would be needed to have 80% power for a NIM of 0.4%, assuming no difference between treatments. The sample size from the study is constrained between a predefined minimum sample size of 258, and a maximum sample size of 400 patients. If the recalculated sample size is smaller than minimum sample size planned, the study will enroll to the minimum sample size. If the recalculated sample size is larger than the planned minimum sample size, the team will make a decision whether to increase sample size to the reestimated sample size, bounded by the predefined maximum, or accept the consequent reduction in power.

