5.2.7. Primary Efficacy Outcome and Methodology

The primary efficacy outcome will be the change in HbA1c level from baseline to 24 weeks. The primary analysis will be a likelihood-based, MMRM approach, treating the data as missing at random (MAR) for the FAS population. The MMRM model will evaluate the change from baseline to each postbaseline visit in HbA1c level as the dependent variable with treatment (LY2963016, Lantus®), pre-study treatment (Lantus®-bolus, other basal-bolus, premixed insulin), and pre-study metformin or acarbose usage (metformin only, acarbose only, or neither), visit, and interaction between visit and treatment as fixed effects; the baseline value of HbA1c as a covariate; and a random effect for patient. The MMRM model will be carried out using the observed margins (OM) option in SAS MIXED procedure. The standard least square means (LSMeans) have equal coefficients across classification effects; however, the OM option changes these coefficients to be proportional to the number of patients used to calculate the classification means. This will provide LSMean estimates that are more representative of the patient population recruited in this study.

The primary treatment comparison is to compare LY2963016 versus Lantus® at the NIM of +0.4%. If the upper limit of the 95% CI on the change from baseline to 24-week endpoint HbA1c for LY2963016 versus Lantus® is below +0.4%, then LY2963016 will be declared noninferior to Lantus®. The LSMean and standard error derived from the MMRM model for each treatment will be used to test noninferiority. Type III sums of squares will be used to make the treatment comparisons.

- If the +0.4% NIM is met, a key secondary treatment comparison will be conducted to show noninferiority of Lantus® to LY2963016. This will be done by comparing Lantus® versus LY2963016 at the NIM of -0.4%. If the lower limit of the 95% CI on the change in HbA1c from baseline to the 24-week endpoint for LY2963016 versus Lantus® is above -0.4%, then Lantus® will be declared noninferior to LY2963016. The LSMean and standard error derived from the MMRM model for each treatment will be used to test noninferiority. This gate-keeping procedure controls the family-wise Type 1 error rate at a 1-sided 0.025 level.

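### The SAP's re-estimation rule, read literally, uses within-patient residual variance instead of the total variance of the Week 24 change, so it can miss an SD above plan.

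*SAP*

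**What the plan says.** SAP 5.1.2, step 2, states the aim: "The residual errors from each model will be used to determine a predictive distribution of the total variability of change in" the primary measure, taken over the whole treatment period. SAP 5.1.2.3 gives the method. Each of 10,000 imputed datasets is analysed with the primary model, leaving out treatment, and the total SD for that dataset is found "by evaluating the residual error of the model". The cross-reference to the primary analysis at this point is broken.

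The primary model in SAP 5.2.7 includes "the baseline value of HbA1c as a covariate; and a random effect for patient". No within-patient covariance structure is stated.

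The prediction model in SAP 5.1.2.3 has two variance components: one for the subject random effect, and one for a within-subject term that the section calls the residual error.

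The resulting SD goes into a two-arm formula, and the recommendation is held between 258 and 400. SAP 5.1.1 sets the target as "80% power for a NIM of 0.4%, assuming no difference between treatments". The formula in 5.1.2.1 and 5.1.2.3 is printed with beta = 0.05, which is 95% power.

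**The concern.** The two-arm formula needs the SD of a single patient's change at Week 24, which contains both between-patient and within-patient variance. In a model with a patient random intercept, the residual holds only the within-patient part. The section itself uses residual error for the within-subject term and gives the subject effect a separate variance. A programmer following the text would therefore enter a number that is not the total variability the SAP names, and no sentence adds the patient variance back.

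The re-estimation is there to detect an SD above the planned 1.05, and a residual-only SD weakens it in exactly that case. Under SAP 5.1.1, a recalculated size below the minimum means enrolling to the minimum. The team's choice to increase arises only when the recalculated size exceeds 258. A falsely low estimate would therefore prompt no discussion. Type I error and the primary analysis are not affected.

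**Working it through.** **Inputs from the documents.** Margin and completers (SAP 5.1.1): "at the 0.40% noninferiority margin (NIM), 109 completers per arm (218 total) are needed at 24 weeks". True difference 0: "This calculation assumes no treatment difference in HbA1c". Error rates: "a two-sided significance level of 0.05, and over 80% power". SD 1.05, dropout 15%, floor 258 and cap 400 (SAP 5.1.1). Allocation 1:1 (protocol 9.3). Beta 0.05 in the formula (SAP 5.1.2.1, 5.1.2.3).

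**Assumed input.** Between-patient share of the total variance: 0.3 to 0.7, not given in the documents.

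**Plan's own figure.** Per arm, n = 2(1.960 + 0.842)² × 1.05² / 0.40² = 108.2, rounded up to 109. Then 109 / 0.85 = 128.2, rounded up to 129, or 258 in total. The plan reproduces.

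**Formulas.**
- SAP formula: N = 4(z₁₋α + z₁₋β)² SD² / 0.16 / 0.85. This is 230.8 × SD² at beta 0.20 and 382.2 × SD² at beta 0.05.
- Residual-only reading: replace SD² by SD² × (1 − share), then clip to 258–400.
- Power at N: Φ(0.4 / (SD × √(2/n)) − 1.96), with n = 0.85N/2. At N = 258 and SD 1.05, n = 109.65 and power = Φ(2.82 − 1.96) = 80.5%.

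**Mechanism.** A random-intercept model was fitted to simulated data (258 patients, four visits, total SD 1.05). The residual SD was 0.90, 0.72 and 0.60 at shares 0.3, 0.5 and 0.7. The fitted total SDs were 1.04, 1.08 and 0.99. The residual does lose the between-patient part, and the raw N shrinks by the factor (1 − share).

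**Result of the residual-only reading.**

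| True SD | N for 80% power (total variance) | Share | Beta 0.05: raw N → recommended (power) | Beta 0.20: raw N → recommended (power) |
|---|---|---|---|---|
| 1.05 | 255 (floor 258) | 0.3 | 295 → 295 (85%) | 178 → 258 (80.5%) |
| | | 0.5 | 211 → 258 (80.5%) | 127 → 258 (80.5%) |
| | | 0.7 | 126 → 258 (80.5%) | 76 → 258 (80.5%) |
| 1.20 | 332 | 0.3 | 385 → 385 (85%) | 233 → 258 (69%) |
| | | 0.5 | 275 → 275 (72%) | 166 → 258 (69%) |
| | | 0.7 | 165 → 258 (69%) | 100 → 258 (69%) |
| 1.35 | 421 (cap 400, 78%) | 0.3 | 488 → 400 (78%) | 295 → 295 (65%) |
| | | 0.5 | 348 → 348 (72%) | 210 → 258 (59%) |
| | | 0.7 | 209 → 258 (59%) | 126 → 258 (59%) |

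**Thresholds.**
- The floor covers 80% power up to SD = √(258 / 230.8) = 1.06.
- The printed beta inflates N by 382.2 / 230.8 = 1.66. This offsets the lost variance up to a share of 1 − 230.8 / 382.2 = 0.40.
- With the total SD and the printed beta, N at SD 1.05 is 382.2 × 1.1025 = 421. The cap is reached at SD = √(400 / 382.2) = 1.02.

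**The case against.** A reader might infer that the SAP definitely drops the between-patient variance and that the recommended size will be far too small. The documents do not support that.

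- **The target is named correctly.** The SAP calls the quantity total variability in both 5.1.2 and 5.1.2.3 and gives it a symbol separate from the two variance components. It never equates it with the within-patient SD. This shows the intent, but the stated computation still does not deliver it.
- **The covariance structure is open.** If the model were fitted with an unstructured residual matrix, the Week 24 residual variance would be the total. That is possible under the MMRM label. However, the text describes a patient random effect, and a separate random intercept cannot be identified alongside an unstructured matrix. The point remains unresolved in the SAP.
- **The floor and the printed beta protect the trial in part.** This stands. At SD 1.05 the size cannot fall below what 80% power needs. With beta 0.05 and a share below about 0.40, the rule still reaches the 80%-power size or the cap. At SD 1.35 and share 0.5 it recommends 348, not the floor, and the loss against the cap is 6 points (72% against 78%). The protection from beta is accidental, though, and goes if beta is aligned with the 80% target.
- **The step is optional and non-binding, and the SAP says it was evaluated by simulation.** The simulation report is not available, so it cannot show which variance was used. Non-binding status helps little when a low estimate gives the team no reason to increase.

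**Conclusion.** The stated rule does not compute the quantity that the SAP names and the formula needs. It should be corrected, but the harm is conditional.

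At the planned SD the 80% target is met. With the printed beta, a shortfall needs both an SD above about 1.06 and a between-patient share above about 0.40. It is then 8 to 11 points below 80% at SD 1.2 (shares 0.5 and 0.7). At SD 1.35 it is 6 to 19 points below the 78% available at the cap.

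At the 80% target of SAP 5.1.1 the rule recommends no increase at SD 1.2 for any share from 0.3 to 0.7 (69% power), nor at SD 1.35 for shares 0.5 to 0.7 (59%).

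These figures rest on the assumed share, a random-intercept reading of the primary model, a true difference of zero and 15% dropout.

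**What to change.** In SAP 5.1.2 (step 2) and 5.1.2.3, define the SD for each imputed dataset as the marginal (total) SD of the Week 24 change given the model covariates. Two ways to obtain it:

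- the residual SD of a Week 24 ANCOVA on the same covariates, with no treatment or patient effect; or
- the square root of the Week 24 diagonal element of an unstructured covariance matrix.

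Adding the random-effect and residual variances of a constant-variance model is not a safe substitute. That sum averages over visits, while the SAP's own prediction model lets variance change with time.

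State the covariance structure of the primary model in SAP 5.2.7 and repair the cross-reference in 5.1.2.3.

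Make this change together with a decision on beta 0.05 (5.1.2.1, 5.1.2.3) against 80% power (5.1.1). Correcting the SD alone, with beta left at 0.05, would recommend the cap of 400 at any SD above 1.02, including the planned 1.05. Correcting beta alone would expose the full shortfall in the last column of the table.

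The cost is SAP wording and a small code change, made before the blinded snapshot.

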5.1.2.4. Determination of the Final Sample Size

The recommended sample size, \hat{N} , is non-binding, but the study team will use the recommendation when making the decision regarding the final sample size. The decision on the final sample size will consider the impact of the recommended sample size on two primary factors, 1) the feasibility of attaining the recommended sample size given the observed enrollment rate, and 2) the degree of certainty in the recommended sample size. Regardless of this decision process, the final target sample size will be no smaller than approximately N_{\min} (258 for this study) and no larger than approximately N_{\max} (400 for this study).

5.2. Statistical and Analytical Plans

5.2.1. General Considerations

All data will be entered, verified, and archived at a contract research organization (CRO) external to Lilly and/or at Lilly. Data listings, summaries, and analyses will be performed by a CRO and/or by Lilly under the guidance and approval of statisticians at Lilly. Statistical analysis of this study will be the responsibility of Lilly.

Any change to the data analysis methods described in the protocol will require an amendment ONLY if it changes a principal feature of the protocol. Any other change to the data analysis methods described in the protocol, and the justification for making the change, will be described in the statistical analysis plan and/or in the clinical study report (CSR). Additional exploratory analyses will be conducted, as deemed appropriate.

The patient populations used in the study are described below:

1. All Patients Entered: all patients who entered this study and completed Visit 1.
2. All Randomized: all patients who were randomized to a treatment arm.
3. Full Analysis Set (FAS): based on the intent to treat (ITT) principle, all patients who were randomized and who have taken at least one dose of study medication. Patients are assigned to the treatment arm to which they were randomized.
4. Per-protocol (PP): patients in the FAS/ITT population who also meet the following criteria:
 - a. violate no inclusion or exclusion criteria
 - b. have not discontinued from the study prior to 24 weeks
 - c. have not been off study medication for more than 10 consecutive days during the treatment period
 - d. have not received chronic (lasting longer than 14 consecutive days) systemic glucocorticoid therapy (excluding topical, intra-articular, intraocular, and inhaled preparations)

Unless otherwise specified, listings will be prepared using all randomized patients. Efficacy and safety analyses will be conducted using the FAS population. Selected analyses will be conducted using the All Randomized population and the PP population.

Unless otherwise noted, all tests of treatment effects will be conducted at a 2-sided alpha level of 0.05, and confidence intervals (CIs) will be calculated as 2-sided 95% CIs. All tests of interactions between treatment groups and other factors will be conducted at a 2-sided alpha level of 0.05. No adjustments for multiplicity will be performed. See Section 5.2.7 for the gate-keeping strategies used for primary/secondary endpoints.

The baseline is Visit 2. If baseline data are missing, the last measurement taken prior to this visit will be used for the baseline measurement.

The last visit for the 24-week treatment study is Visit 13. If the Visit 13 measurement is missing, the last post-baseline value will be carried forward to create the 24-week endpoint value using the last-observation-carried-forward (LOCF) methodology. If there are no measurements after Visit 2 (date of randomization), the 24-week endpoint values will be considered missing. If the baseline value is missing or a patient only has a baseline value with no follow-up values, then the patient will not be included in the efficacy analyses. The LOCF methodology will be utilized in the endpoint analyses using analysis of covariance (ANCOVA) of HbA_{1c}, laboratory chemistry and hematology, as well as analysis of hypoglycemia (rate and incidence) and insulin antibodies.

Unless otherwise noted, the analysis of the continuous secondary efficacy and safety variables (SMBG at each time point and summaries of SMBG, weight, dose, and vital signs) will be performed using the same mixed model repeated measures (MMRM) methodology for the primary efficacy analysis with the baseline value of the response variable added as a covariate with the FAS population. Continuous laboratory measures will be analyzed using the ANCOVA model.

Unless otherwise noted, the analysis of categorical variables to compare the 2 treatments will be performed using Fisher's exact test or Pearson's chi-square test.

Values for the 7-point self-monitored blood glucose (SMBG) blood glucose profiles will be averaged over the two 7-point SMBG profiles obtained during 2-week period prior to each office visit (as specified in Protocol Section 7.2.3). For the average blood glucose calculation for a specific time point, if only 1 of 2 days of data is collected, then the value of the 1 day will be used. If 2 days of data are collected, then the average of the 2 days will be used. If more than 2 days of data are collected then choose the 2 according to the ranking first by the number of non-missing blood glucose measurements and then by day closest to the visit day. The handling of missing data for the ITSQ questionnaire is specified in Section 5.2.10.

Visits for laboratory data will be handled by conventions in the Lilly diabetes white paper (Standardization of Derivations for Efficacy Lab Variables).

All analyses will be implemented using SAS Version 8.2[®] or higher.

